17.3. Subject Information and Consent

Prior to performing any study-related activities under this protocol, including screening tests and assessments, written informed consent with the approved ICF must be obtained from the subject or subject's legally authorized representative (e.g., parent or legal guardian), as applicable, in accordance with local practice and regulations.

The background of the proposed study, the procedures, the benefits and risks of the study, and that study participation is voluntary for the subject must be explained to the subject (or the

CONFIDENTIAL

The information contained herein may not be used, disclosed, or published without the written consent of Biogen MA Inc.

subject's legally authorized representative). The subject must be given sufficient time to consider whether to participate in the study.

In addition, subjects who have the capacity should provide their assent to participate in the study. The level of information provided to subjects should match their level of understanding as determined by the Investigator and in accordance with applicable regulations and guidelines.

A copy of the signed and dated ICF and assent if applicable must be given to the subject or the subject's legally authorized representative. The signed and dated ICF will be retained with the study records. Local regulations must be complied with in respect to the final disposition of the original (wet signature) and copies of the signed and dated ICFs.

Confirmation of informed consent and assent if applicable must also be documented in the subject's medical record.

17.4. Subject Data Protection

Prior to any testing under this protocol, including screening tests and assessments, candidates must also provide all authorizations required by local law (e.g., Protected Health Information authorization in North America).

The subject will not be identified by name in the eCRF or in any study reports, and these reports will be used for research purposes only. Biogen, its partners and designees, ethics committees, and various government health agencies may inspect the records of this study. Every effort will be made to keep the subject's personal medical data confidential.

17.5. Compensation for Injury

Biogen maintains appropriate insurance coverage for clinical studies and will follow applicable local compensation laws.

17.6. Conflict of Interest

The Investigators should address any potential conflicts of interest (e.g., financial interest in Biogen or partnering company) with the subject before the subject makes a decision to participate in the study.

17.7. Registration of Study and Disclosure of Study Results

Biogen will register the study and post study results regardless of outcome on a publicly accessible website in accordance with the applicable laws and regulations.

CONFIDENTIAL

The information contained herein may not be used, disclosed, or published without the written consent of Biogen MA Inc.

18. ADMINISTRATIVE PROCEDURES

18.1. Study Site Initiation

The Investigator must not enroll any subjects prior to completion of a study initiation visit conducted by Biogen. This initiation visit will include a detailed review of the protocol and study procedures.

18.2. Quality Assurance

During and/or after completion of the study, quality assurance officers named by Biogen or the regulatory authorities may wish to perform onsite audits or inspections. The Investigator will be expected to cooperate with any audit or inspection and to provide assistance and documentation (including source data) as requested.

18.3. Monitoring of the Study

The Investigator must permit study-related monitoring by providing direct access to source data and to the subjects' medical histories.

The Clinical Monitor will visit the Investigator at regular intervals during the study and after the study has completed, as appropriate.

During these visits, eCRFs and supporting documentation related to the study will be reviewed and any discrepancies or omissions will be resolved.

Monitoring visits must be conducted according to the applicable ICH and GCP guidelines to ensure protocol adherence, quality of data, study treatment accountability, compliance with regulatory requirements, and continued adequacy of the investigational site and its facilities.

18.4. Study Funding

Biogen is the Sponsor of the study and is funding the study. All financial details are provided in the separate contracts between the institution, Investigator, and Biogen.

18.5. Publications

Details are included in the clinical trial agreement for this study.

CONFIDENTIAL

The information contained herein may not be used, disclosed, or published without the written consent of
Biogen MA Inc.

19. FURTHER REQUIREMENTS AND GENERAL INFORMATION

19.1. External Contract Organizations

Biogen will be responsible for all administrative aspects of this study including but not limited to study initiation, monitoring, management of AEs, and data management.

19.1.1. Contract Research Organization

A contract research organization (CRO), [REDACTED], will be jointly responsible for administrative aspects of the study including but not limited to study initiation, monitoring, and management of SAE reports and data management. Before subjects are screened at each study site, the CRO will review study responsibilities with the Investigators and other study site staff, as appropriate.

19.1.2. Electronic Data Capture

Subject information will be captured and managed by study sites on eCRFs by a Web-based electronic data capture tool OR remote data capture tool developed and supported by iMedidata RAVE and configured by [REDACTED].

19.1.3. Central Laboratories for Laboratory Assessments

A central laboratory has been selected by Biogen to analyze all safety laboratory samples collected for this study.

19.1.4. Central Facility for Other Assessments

Central and specialty facilities have been selected by Biogen to read and interpret all MRI scans for this study.

19.2. Study Committees

19.2.1. Advisory Committee

An advisory committee will be formed to provide scientific and medical direction for the study and to oversee the administrative progress of the study. The advisory committee will conduct regular reviews to monitor subject accrual and to monitor compliance with the protocol at individual study sites. The advisory committee will determine whether the study should be stopped or amended for reasons other than safety.

Members of the advisory committee will include the Medical Director, Clinical Operations Lead, and Project Statistician from Biogen, and participating Investigators. Biogen will designate one of the participating Investigators to be the chairperson of the advisory committee.

CONFIDENTIAL

The information contained herein may not be used, disclosed, or published without the written consent of Biogen MA Inc.

19.2.2. Independent Data Monitoring Committee

An Independent Data Monitoring Committee (IDMC) will monitor the progress of the study, review interim safety data, and oversee the safety of subjects participating in this study. The specifics regarding the IDMC organization and procedures will be outlined in the IDMC Charter.

19.3. Changes to Final Study Protocol

Protocol modifications that affect subject safety, the scope of the investigation, or the scientific quality of the study must be approved by the ethics committee before implementation of such modifications to the conduct of the study. If required by local law, such modifications must also be approved by the appropriate regulatory agency prior to implementation.

However, Biogen may, at any time, amend this protocol to eliminate an apparent immediate hazard to a subject. In this case, the appropriate regulatory authorities will be notified subsequent to the modification.

In the event of a protocol modification, the ICF may require corresponding modifications (see Section 17).

19.4. Ethics Committee Notification of Study Completion or Termination

Where required, the regulatory authorities and ethics committees must be notified of completion or termination of this study, and sent a copy of the study synopsis in accordance with necessary timelines.

19.5. Retention of Study Data

The minimum retention time for study records will meet the strictest standard applicable to that site, as dictated by any institutional requirements or local laws or regulations. Prior to proceeding with destruction of records, the Investigator must notify Biogen in writing and receive written authorization from Biogen to destroy study records. In addition, the Investigator must notify Biogen of any changes in the archival arrangements including but not limited to archival at an offsite facility or transfer of ownership if the Investigator leaves the site.

19.6. Study Report Signatory

Biogen will designate 1 or more of the participating Study Investigators as a signatory for the study report. This determination will be made by several factors, including but not limited to, the Investigator's experience and reputation in the studied indication; the Investigator's contribution to the study in terms of design, management, and/or subject enrollment; or by other factors determined to be relevant by Biogen.

CONFIDENTIAL

The information contained herein may not be used, disclosed, or published without the written consent of Biogen MA Inc.

### List of Abbreviations

AE	adverse event
BID	twice daily
CDT	Clinical Development Team
CI	confidence interval
CRF	case report form
CRO	contract research organization
DMF	dimethyl fumarate
EDC	electronic data capture
GCP	Good Clinical Practice
ICF	informed consent form
ICH	International Council on Harmonisation
IFN	interferon
IgG	immunoglobulin G
IXRS	Interactive Voice/Web Response System
MCV4	meningococcal polysaccharide diphtheria conjugate vaccine (quadrivalent)
MedDRA	Medical Dictionary for Regulatory Activities
MS	multiple sclerosis
PHI	protected health information
PPSV23	23-valent pneumococcal polysaccharide vaccine
RRMS	relapsing-remitting multiple sclerosis
SAE	serious adverse event
SMT	Study Management Team
SUSAR	suspected unexpected serious adverse reaction
Td	tetanus diphtheria toxoids vaccine
US	United States
WHO	World Health Organization

## **1 STUDY OBJECTIVES AND ENDPOINTS**

### **1.1 Primary Objective and Endpoint**

The primary objective of the study is to evaluate the long-term safety of BG00012 in pediatric subjects who completed Study 109MS202.

Primary endpoint:

incidence of AEs, serious AEs (SAEs), and discontinuations of study treatment due to an AE

### **1.2 Secondary Objectives and Endpoints**

The secondary objectives of this study are as follows:

- to evaluate the long-term efficacy of BG00012
- describe the long-term MS outcomes in subjects who completed Study 109MS202

The secondary endpoints are:

- The total number of new or newly enlarging T2 hyperintense lesions on brain MRI scans, the ARR, and the proportion of subjects who experience 1 or more relapses during the study period.
- The degree of disability as measured by the EDSS and disability progression (as measured by at least a 1.0-point increase on the EDSS from baseline EDSS  $\geq 1.0$  that is sustained for 24 weeks, or at least a 1.5-point increase on the EDSS from baseline EDSS = 0 that is sustained for 24 weeks).

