7.2.3. Follow-Up

Subjects are to return to the study site for a follow-up visit 4 weeks after their last treatment visit (Visit 10 at Week 96 [± 5 days]).

Subjects who withdraw prematurely from the study will complete the Early Withdrawal Visit, which should be conducted as soon as possible and no later than 4 weeks after the subject's last dose of study treatment. Subjects who withdraw prematurely should be encouraged to complete the Safety Follow-Up Visit 4 weeks after the last dose of study treatment.

Subjects who complete, temporarily withhold, or permanently discontinue study treatment for any reason and have a lymphocyte count less than the lower limit of normal (LLN) will be followed every 4 weeks for 24 weeks and then every 3 months (**unless clinically indicated more often or at the Investigator's discretion**) until the lymphocyte count is \geq LLN or for 52 weeks after the last dose, or until one of the following occurs: 1) the subject continues on commercial BG00012 following study withdrawal/completion, or 2) the subject is initiated on another MS disease-modifying therapy.

CONFIDENTIAL

The information contained herein may not be used, disclosed, or published without the written consent of
Biogen MA Inc.

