10. DISCONTINUATION OF STUDY TREATMENT AND/OR WITHDRAWAL OF SUBJECTS FROM THE STUDY

10.1. Discontinuation of Study Treatment

A subject *must* permanently discontinue BG00012 for any of the following reasons:

- The subject becomes pregnant. Study treatment must be discontinued immediately. Report the pregnancy according to the instructions in Section [15.4.1](#).
- The subject experiences a medical emergency that necessitates permanent discontinuation of study treatment.
- The subject has lymphocyte count $<500/\text{mm}^3$ for 6 months as outlined in [Table 4](#) and [Table 5](#).
- The subject experiences a protocol-specified change in laboratory values that necessitates permanent discontinuation of treatment as outlined in [Table 3](#) and [Table 4](#).
- The subject cannot tolerate study treatment.
- The subject receives any of the disallowed concomitant medications for this study.
- The subject or subject's parent/legal guardian desires to discontinue treatment.
- At the discretion of the Investigator for medical reasons or for noncompliance.

The reason for discontinuation of study treatment must be recorded in the subject's eCRF.

Subjects who discontinue treatment may remain in the study and continue protocol-required tests and assessments.

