11.5.1.2. Disallowed Concomitant Therapy

Concomitant treatment with any of the following is not allowed while receiving study treatment, unless approved by the Medical Monitor, or as otherwise described in this protocol:

- Any alternative drug treatments directed toward the treatment of MS, such as immunomodulatory treatments (including but not limited to, interferon-beta, glatiramer acetate, natalizumab, fingolimod, teriflunomide, alemtuzumab, mitoxantrone, mycophenolate mofetil, laquinimod, cyclophosphamide, methotrexate, azathioprine, cyclosporine, etc.) and 4-aminopyridine or related products with the exception of acute management of protocol-defined relapse (as described in Section 11.5.2).
- Any investigational product, including investigational symptomatic therapies for MS and investigational therapies for non-MS indications.
- Any systemic steroid therapy including but not limited to, oral corticosteroids (e.g., prednisone) or periodic (e.g., monthly) treatment with IVMP, except for protocol-defined treatment of relapses as described in Section 11.5.2. Steroids that are administered by nonsystemic routes (e.g., topical, inhaled) are allowed.
- Total lymphoid irradiation, cladribine, T-cell or T-cell receptor vaccination, any therapeutic monoclonal antibody, intravenous (IV) immunoglobulin, plasmapheresis, or cytapheresis.

Subjects who receive any of these restricted medications without approval from the Biogen Medical Director(s) will be required to permanently discontinue study treatment and will be withdrawn from the study as outlined in Section 10.2.

CONFIDENTIAL

The information contained herein may not be used, disclosed, or published without the written consent of Biogen MA Inc.

Use of the concomitant therapies or procedures defined above must be recorded on the subject's eCRF, according to the instructions for eCRF completion. AEs related to the administration of these therapies or procedures must be documented on the appropriate eCRF.

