### **2.2 Overall Study Duration and Follow-Up**

The study period will consist of enrollment, treatment, and follow-up. The study duration is approximately 104 weeks, consisting of a 4-week enrollment period (if the Final Study Visit from Study 109MS202 cannot be combined with the Baseline Visit for this study), a 96-week treatment period, and a Safety Follow-Up Visit up to 4 weeks after the last dose of study treatment. Unscheduled Relapse Assessment Visits and Lymphocyte Follow-Up Visits will be performed as necessary.

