### **6.2.2 Analysis Methods**

Summary statistics will be presented for MRI data (number of new or newly enlarging T2 hyperintense lesions) over time

ARR will be summarized, along with the proportion of subjects relapsing, the rate of relapses requiring IV steroid use, and the rate of MS-related hospitalizations.

EDSS scores and changes from baseline will be summarized over time along with the proportion of subjects with confirmed disability progression.

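### The SAP does not limit the relapse endpoints to time on BG00012 and gives the ARR no window, numerator or denominator

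*SAP*

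**What the plan says.** The secondary objective in SAP 1.2 is "to evaluate the long-term efficacy of BG00012". The relapse endpoints under it are "the ARR, and the proportion of subjects who experience 1 or more relapses during the study period". The time window follows the proportion relapsing; the ARR is named without one.

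SAP 2.2 states: "The study period will consist of enrollment, treatment, and follow-up". It continues: "The study duration is approximately 104 weeks, consisting of a 4-week enrollment period", followed by 96 weeks of treatment and a Safety Follow-Up Visit no more than 4 weeks after dosing ends. Under End of Study for Subjects, SAP 2.2 names that visit as the final data collection.

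The whole ARR method in SAP 6.2.2 is "ARR will be summarized, along with the proportion of subjects relapsing", with the rates of steroid-treated relapses and MS-related hospitalizations. SAP 6.2.1 requires one dose and an evaluation, and sets no on-treatment limit. SAP section 6 gives the default summary for continuous endpoints: mean, standard deviation, median and range.

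Protocol v3.0, section 10.1, says: "Subjects who discontinue treatment may remain in the study and continue protocol-required tests and assessments". Section 11.5.1.2 restricts other MS drugs as follows: "Concomitant treatment with any of the following is not allowed while receiving study treatment".

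**The concern.** The study has one arm, so the ARR is itself the efficacy result, and no control group shares whatever distortion the counting rules bring in. An objective about BG00012 calls for a rate that can be tied to BG00012 exposure. As written, a programmer could count relapses and person-time to the last dose, to Week 96, to the Safety Follow-Up Visit or beyond, and each choice would comply with the SAP.

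Time after stopping could raise the ARR if relapses return, or lower it if the subject moves to another effective drug. A reader of the report could not tell which had happened. The start is open too, because the study period includes enrollment.

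The SAP does set such an anchor for safety: SAP 6.3.2.2 counts adverse events as treatment-emergent from the first 109MS311 dose. It also reports completing treatment and completing the study as separate counts (SAP 6.1.2), so it recognises that the two can differ. The relapse endpoints get no matching rule.

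**Working it through.** **1. The plan's own figure.** Enrollment 4 + treatment 96 + follow-up 4 = 104 weeks, which matches SAP 2.2. The lymphocyte follow-up of up to 52 weeks is not in this total. The documents give no expected ARR, stopping rate or calculated sample size, so all sizes below are illustrations.

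**2. Can off-drug and other-drug time enter?** Protocol 10.1 lets a subject stay after stopping. Protocol 11.5.1.2 bars other MS drugs only during study treatment. That section also says unapproved users will be withdrawn under section 10.2, but section 10.2 does not list that reason, and section 10.1 lists disallowed medication as a reason to stop treatment before saying that subjects who stop may remain. The clear route is therefore a subject who has already stopped, stays, and then starts another drug. No rule in SAP 6.2 censors at either event.

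**3. Effect of time after stopping.** Assume a share p stops at week s, all stoppers stay to Week 96, everyone else is treated to Week 96, and rates are constant. Let k be the off-drug rate divided by the on-drug rate.

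- Off-drug share of person-time: w = p × (96 − s)/96
- Pooled whole-study ARR ÷ on-drug ARR = 1 − w + w × k

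For p = 0.20 and s = 24: w = 0.20 × 72/96 = 0.15. With k = 0.2 the ratio is 0.85 + 0.03 = 0.88; with k = 3 it is 0.85 + 0.45 = 1.30.

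| Share stopping | Stop week | w | Ratio, k = 0.2 | Ratio, k = 3 |
|---|---|---|---|---|
| 10% | 24 | 0.075 | 0.94 | 1.15 |
| 10% | 48 | 0.050 | 0.96 | 1.10 |
| 20% | 24 | 0.150 | 0.88 | 1.30 |
| 20% | 48 | 0.100 | 0.92 | 1.20 |
| 30% | 24 | 0.225 | 0.82 | 1.45 |
| 30% | 48 | 0.150 | 0.88 | 1.30 |

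**4. Effect of the Safety Follow-Up weeks.** For a completer, 4/100 = 4% of the time from first dose falls after the last dose. The ratio is 0.96 + 0.04 × 2 = 1.04 at k = 2 and 0.96 + 0.04 × 3 = 1.08 at k = 3. Protocol 11.6 allows commercial BG00012 in this period, so even this time is not always off drug.

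**5. Weighting.** The SAP does not say whether ARR is pooled or averaged over subjects. As a constructed example, take 19 subjects followed for 96 weeks with 9 relapses in all, and one who relapses and leaves at Week 8.

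- Pooled: 10 relapses ÷ ((19 × 96 + 8)/52.18 years) = 10/35.11 = 0.285
- Mean of subject ARRs: (9 × 52.18/96 + 52.18/8)/20 = (4.89 + 6.52)/20 = 0.571

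The two readings differ by a factor of 2 because the 8-week subject counts as much as a 96-week subject.

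**The case against.** The strongest reply is that the documents leave the ARR under-specified; they do not show it to be wrong. That is right. In SAP 1.2 the study period is attached to the proportion relapsing, so a reader who concludes that the ARR must run over the whole study period goes beyond the text.

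A reader might also infer that 52 weeks of lymphocyte follow-up are counted. SAP 2.2 points the other way: it ends the study for subjects at the Safety Follow-Up Visit, and its 104 weeks leave no room for them. Because the same section mentions lymphocyte visits as needed, the boundary is unclear, but inclusion is not established. Read literally, that end point would also close follow-up within 4 weeks of an early last dose. This sits awkwardly with Protocol 10.1, so long counted off-drug time is possible, not certain.

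Nor can lymphocyte follow-up under Protocol v3.0 be time on another MS drug. It ends when "the subject is initiated on another MS disease-modifying therapy" (Protocol 7.2.3). Relapse assessment is missing from the lymphocyte visit column, but it is equally missing from every scheduled visit in Table 1. Relapses are found through symptom-triggered contact (Protocol 7.3), so its absence does not show that relapses go unseen.

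The averaging problem is conditional: section 6 describes what summaries generally include, and nothing says ARR will be computed per subject. The example is deliberately extreme.

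Finally, counting all on-study relapses regardless of stopping is a legitimate choice, and the ARR is a descriptive secondary endpoint in a study whose primary endpoint is safety. This limits the weight of the point, but the choice still has to be stated.

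**Conclusion.** The point holds as a gap in specification. The relapse endpoints are not limited to time on BG00012, the ARR has no stated window, numerator or denominator, and nothing handles relapses after stopping or after another MS drug is started. The plan therefore allows an efficacy result that mixes exposures; it does not establish that the reported ARR will do so.

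The size cannot be fixed from the documents. With 20% stopping and all of them staying to Week 96, and an off-drug rate 0.2 to 3 times the on-drug rate, the whole-study ARR is 0.88 to 1.30 times the on-drug ARR for stopping at Week 24 and 0.92 to 1.20 times for Week 48. The effect shrinks if fewer stop or if stoppers leave the study. The low end depends on the narrow route of stopping, staying and then taking another effective drug.

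**What to change.** In SAP 6.2.2, report two ARR lines side by side. Each is total protocol-defined relapses divided by total person-years over the same interval, with a 95% confidence interval by a named method.

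- **(a) On-treatment:** from the first to the last 109MS311 dose, or to the start of another MS drug if earlier.
- **(b) Whole-study:** from the first 109MS311 dose to the later of the Week 96 assessment and the Safety Follow-Up Visit, or to withdrawal if earlier, excluding time that is lymphocyte follow-up only.

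Give the proportion relapsing by Week 96 as a Kaplan-Meier estimate beside the crude proportion, and state the window for each.

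Two passages need reconciling as well. SAP Table 2 (Additional Study Activities), footnote 3, lacks the end points for lymphocyte follow-up that Protocol v3.0 gives in its own Table 2, footnote 3. Protocol 11.5.1.2 refers to section 10.2 for a withdrawal reason that section 10.2 does not list.

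The cost is SAP wording and one extra table; dosing and concomitant-therapy data are already collected. Line (a) has slightly less person-time, and its censoring may be informative if subjects stop because of disease activity. Line (b) is kept for that reason.
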